## **12. PROCEDURE FOR HANDLING PRODUCT QUALITY COMPLAINTS**

A Product Quality Complaint (PQC) refers to any written, electronic, or oral communication that alleges deficiencies related to the identity, quality, durability, reliability, safety, effectiveness or performance of test articles after they have been released for clinical trial use.

Potential complaints may come from a variety of sources including but not limited to subjects, clinical research associates (CRA), clinical operations managers (COM), medical monitors, and site personnel, etc. The following are not considered product quality complaints:

- Subject satisfaction inquiries reported via “Subjective Questionnaires” and “Patient Reported Outcomes (PRO)”
- Clinical test articles that are stored improperly or damaged after receipt at the investigational site
- Artificial tear replacements that occur due to loss/run out
- Damage deemed by clinicians or clinical staff to be caused by handling by the user, and not indicative of a quality deficiency, only in situations where there is no deficiency alleged by the subject

Within 24 hours of site personnel becoming aware that a PQC has occurred, the PQC must be recorded in the EDC system, which will trigger an automatic email notification to the appropriate COM/CRA and Clinical QA representative. In cases where the EDC system in use is not configured to send automatic notifications or when an EDC system is not used, the COM/CRA is responsible for notifying Clinical QA upon discovery that a PQC has occurred.

Upon receipt of the EDC notification, the COM/CRA will contact the study site to collect additional information which will include:

- Date the complaint was received/recorded in the EDC System (Date of Sponsor Awareness)
- Who received the complaint
- Study number
- Clinical site information (contact name, site ID, telephone number)
- Lot number(s)
- Unique Subject Identifier(s)
- Indication of who first observed complaint (site personnel or subject)
- OD/OS indication, along with whether the drops were inserted
- Any related AE number, if applicable
- Detailed complaint description (scheduled/unscheduled visit, symptoms, resolution of symptoms, etc.)
- Eye Care Provider objective (slit lamp) findings if applicable
- Confirmation of product availability for return (and tracking information, if available), or rationale if product is not available for return (Refer to [REDACTED] [REDACTED] for test article return instructions)

Once a complaint is received, it will be assessed by the COM, CRA, or trained site personnel to determine if it is an Adverse Event/Serious Adverse Event (AE/SAE). If the complaint results in an AE/SAE, the COM/CRA, or trained site personnel will follow Section 13 of this protocol. If the AE/SAE was potentially the result of a product quality related deficiency, these procedures also applies and will be executed in parallel.

In some cases, a PQC form may be generated in EDC by the site in error. In this event, the PQC forms will be marked “Intentionally Left Blank” or “ILB”. Justification for ILB must be documented.

## 13. ADVERSE EVENTS

### 13.1. Definitions and Classifications

**Adverse Event (AE)** – An AE is “any untoward medical occurrence, unintended disease or injury, or untoward clinical signs (including abnormal laboratory findings) in subjects, users or other persons, whether or not related to the investigational medical device.

*Note 1 to entry:* This definition includes events related to the investigational medical device or the comparator.

*Note 2 to entry:* This definition includes events related to the procedures involved.

*Note 3 to entry:* For users or other persons, this definition is restricted to events related to investigational medical devices.”

An AE includes any condition (including a pre-existing condition) that:

1. Was not present prior to the study, but appeared or reappeared following initiation of the study
2. Was present prior to the study, but worsened during the study. This would include any condition resulting from concomitant illnesses, reactions to concomitant medications, or progression of disease states
3. Pregnancy must be documented as an adverse event and must be reported to the clinical monitor and to the Sponsor immediately upon learning of the event

**Serious Adverse Event (SAE)** – An SAE is any untoward medical occurrence that:

- Results in death
- Is life threatening
- Requires in-patient hospitalization or prolongation of existing hospitalization
- Results in persistent or significant disability/incapacity (e.g., a sight threatening event, a significant persistent or permanent change, impairment, damage, or disruption to the subject's body)
- Is a congenital anomaly/birth defect, or
- Requires intervention to prevent permanent damage (the use of the test article resulting in a condition which requires medical or surgical intervention to preclude permanent impairment of the body structure or a body function). Important medical events that may not result in death, be life-threatening, or require hospitalization may be considered an SAE when, based upon appropriate medical judgment, they may jeopardize the patient or subject and may require medical or surgical intervention to prevent one of the outcomes listed in the above definition

Diagnoses and conditions that are considered Ocular Serious Adverse Events include, but not limited to:

- Microbial Keratitis (MK)
- Iritis (including cells in the anterior chamber)
- Permanent decrease in best spectacle corrected visual acuity equivalent to 2 acuity lines or greater
- Central Corneal Opacity
- Central Corneal Neovascularization
- Uveitis
- Endophthalmitis
- Hypopyon
- Hyphemia
- Penetration of Bowman's Membrane
- Persistent Epithelial Defect
- Limbal cell Damage leading to Conjunctivalization

**Significant Adverse Events** – Those events that are usually symptomatic and warrant discontinuation (temporary or permanent) of the test article (excluding Serious Adverse Events).

Diagnoses and conditions that are considered Ocular Significant Adverse Events include, but not limited to the following:

- Significant Infiltrative Events (SIE)
- Keratoconjunctivitis (toxic or infectious)
- Chemical Keratitis
- Any Temporary Loss of >2 Lines of BSCVA
- Other Grade 3 or higher corneal findings, such as abrasions or edema
- Corneal events - e.g. Epidemic Keratoconjunctivitis (EKC)
- Asymptomatic Corneal Scar
- Any corneal event which necessitates temporary lens discontinuation >2 weeks

**Non-Significant Adverse Events** – Those conditions that are usually asymptomatic and usually do not warrant discontinuation (temporary or permanent) of the test article. However, the Investigator may choose to treat as a precautionary measure.

Diagnoses and conditions that are considered Ocular Non-Significant Adverse Events include, but not limited to the following:

- Non-significant Infiltrative Event (NSIE)
- Papillary Conjunctivitis
- Corneal abrasions
- Superficial Punctate Keratitis (SPK)
- Conjunctivitis: Bacterial, Viral, Allergic
- Blepharitis
- Meibomianitis
- Contact Dermatitis
- Localized Allergic Reactions or infections
- Temporary visual disturbances (blurriness)
- Any corneal event not explicitly defined as serious or significant adverse event, which necessitates temporary discontinuation of the drops <2 weeks

**Adverse Device Effect (ADE)** – An ADE is an “adverse event related to the use of an investigational medical device.

*Note 1 to entry:* This definition includes adverse events resulting from insufficient or inadequate instructions for use, deployment, implantation, installation, or operation, or any malfunction of the investigational medical device.

*Note 2 to entry:* This definition includes any event resulting from use error or from intentional misuse of the investigational medical device.”

**Unanticipated Adverse Device Effect (UADE)** – Any serious adverse effect on health or safety or any life-threatening problem or death caused by, or associated with, the test article, if that effect, problem, or death was not previously identified in nature, severity, or degree of incidence in the investigational plan, Investigator’s Brochure or protocol, or any other unanticipated serious problem associated with the test article that relates to the rights, safety and welfare of subjects.

### 13.2. Assessing Adverse Events

In conjunction with the medical monitor, the Investigator will evaluate adverse events to ensure the events are categorized correctly. Elements of categorization will include:

- Seriousness/Classifications (see definition in Section 13.1)
- Causality or Relatedness – i.e. the relationship between the test article, study treatment or study procedures and the adverse event (not related; unlikely related; possibly related; related - see definition in Section 13.2.1)
- Adverse Event Severity – Adverse event severity is used to assess the degree of intensity of the adverse event (mild; moderate; severe for all events - see definition in Section 0)
- Outcome – not recovered or not resolved; recovering or resolving; recovered or resolved with sequelae; recovered or resolved; death related to adverse event; unknown
- Actions Taken – none; temporarily discontinued; permanently discontinued; other

### 13.2.1. Causality Assessment

**Causality Assessment** – A determination of the relationship between an adverse event and the test article. The test article relationship for each adverse event should be determined by the investigator using these explanations:

- Not Related- An adverse event that is not related to the use of the test article, study treatment or study procedures
- Unlikely Related – An adverse event for which an alternative explanation is more likely, e.g. concomitant treatment, concomitant disease(s), or the relationship of time suggests that a causal relationship is not likely
- Possibly Related – An adverse event that might be due to the use of the test article, or to the study treatment or study procedures. An alternative explanation, e.g. concomitant treatment, concomitant disease(s), is inconclusive. The relationship in time is reasonable. Therefore, the causal relationship cannot be excluded
- Related – An adverse event that is listed as a possible adverse effect (device) or adverse reaction (drug) and cannot be reasonably explained by an alternative explanation, e.g. concomitant treatment of concomitant disease(s). The relationship in time is very suggestive, e.g. it is confirmed by de-challenge and re-challenge

### 13.2.2. Severity Assessment

**Severity Assessment** – A qualitative assessment of the degree of intensity of an adverse event as determined by the Investigator or reported to him/her by the subject. The assessment of severity is made irrespective of test article, study treatment or study procedure relationship or seriousness of the event and should be evaluated according to the following scale:

- Mild – Event is noticeable to the subject, but is easily tolerated and does not interfere with the subject’s daily activities
- Moderate – Event is bothersome, possibly requiring additional therapy, and may interfere with the subject’s daily activities
- Severe – Event is intolerable, necessitates additional therapy or alteration of therapy and interferes with the subject’s daily activities

### 13.3. Documentation and Follow-Up of Adverse Events

The recording and documenting of adverse events (ocular and non-ocular) begins when the subjects are exposed to the test article, study treatment or study procedure. Adverse events reported before the use of test article, start of study treatment, or study procedures will be recorded as medical history. However, if the condition deteriorates at any time during the study it will be recorded and reported as an AE. Untoward medical events reported after the subject’s exit from the study will be recorded as adverse events at the discretion of the Investigator.

Upon finding an adverse event, the Principal Investigator will document the condition in the subject record and in the eCRFs. He/she will complete the Adverse Event /eCRF.

Complete descriptions of all adverse events must be available in the subject record. All Adverse Events including local and systemic reactions not meeting the criteria for “serious adverse events” shall be captured on the appropriate case report form or electronic data system. All adverse events occurring while the subject is enrolled in the study must be documented appropriately regardless of relationship.

It is the Investigator's responsibility to maintain documentation of each reported adverse event. All adverse events will be followed in accordance with applicable licensing requirements. Such documentation will include the following:

- Adverse event (diagnosis not symptom)
- Drawings or photographs (where appropriate) that detail the finding (e.g., size, location, and depth, etc.)
- Date the clinical site was notified
- Date and time of onset
- Date and time of resolution
- Adverse event classification, severity, and relationship to test articles, as applicable
- Treatment regimen instituted, including concomitant medications prescribed, in accordance with applicable licensing requirements
- Any referral to another health care provider if needed
- Outcome, ocular damage (if any)
- Likely etiology
- Best corrected visual acuity at the discovery of the event and upon conclusion of the event

In addition, if an infiltrate(s) is present, he/she will complete the Corneal Infiltrate Assessment eCRF. Where necessary, a culture of the corneal lesion will be collected to determine if the infection is microbial in nature. If cultures are collected, the date of culture collection and laboratory utilized will be recorded.

Changes in the severity of an AE shall be documented to allow an assessment of the duration of the event at each level of intensity to be performed. Adverse events characterized as intermittent require documentation of the onset and duration of each episode. Changes in the assessment of relationship to the Test Article shall also be clearly documented.

Subjects who present with an adverse event shall be followed by the Investigator, within licensure, until all signs and symptoms have returned to pre-treatment status, stabilized, or been satisfactorily resolved. If further treatment beyond licensure is required, the patient will be referred to the appropriate health care provider. The Investigator will use his/her clinical judgment as to whether a subject reporting with an adverse event will continue in the study. If a subject is discontinued from the study, it will be the responsibility of the Investigator to record the reason for discontinuation. The Investigator will also document the adverse event appropriately and complete the Adverse Event eCRF. Any subjects with ongoing adverse events related to the test article, study treatment or study procedures, as of the final study visit date, should be followed to resolution of the adverse event or until referral to an appropriate health care provider, as recommended by the Investigator. Non-ocular adverse events that are not related to the test article, study treatment, or study procedures may be recorded as "ongoing" without further follow-up.

#### **13.4. Reporting Adverse Events**

The Investigator will notify the Sponsor of an adverse event by e-mail, facsimile, or telephone as soon as possible and no later than 24 hours from discovery for any serious /significant adverse events, and 2 days from discovery for any non-significant adverse event. In addition, a written report will be submitted by the Principal Investigator to the

IEC/IRB according to their requirements (Section 13.4.2). The report will comment whether or not the adverse event was considered to be related to the test article, study treatment or study procedures.

#### **13.4.1. Reporting Adverse Events to Sponsor**

##### **Serious/Significant Adverse Events**

The Investigator will inform the sponsor of all serious/significant adverse events occurring during the study period as soon as possible by e-mail, fax, or telephone, but no later than 24 hours following discovery of the event. The Investigator is obligated to pursue and obtain information requested by the Sponsor in addition to that information reported on the eCRF. All subjects experiencing a serious/significant adverse event must be followed up and all outcomes must be reported.

When medically necessary, the Investigator may break the randomization code to determine the identity of the treatment that the subject received. The Sponsor and study monitor should be notified prior to unmasking the test articles.

In the event of a serious/significant adverse event, the Investigator must:

- Notify the Sponsor immediately
- Obtain and maintain in the subject's records all pertinent medical information and medical judgment for colleagues who assisted in the treatment and follow-up of the subject
- Provide the Sponsor with a complete case history which includes a statement as to whether the event was or was not related to the use of the test article
- Notify the IEC/IRB as required by the IEC/IRB reporting procedure according to national regulations

##### **Unanticipated (Serious) Adverse Device Effect (UADE)**

In the event of an Unanticipated (Serious) Adverse Device Effect (UADE), the Investigator will submit a report of the UADE to the Sponsor and IEC/IRB as soon as possible, but no later than 24 hours after the Investigator first learns of the effect. This report is in addition to the immediate notification mentioned above.

The Sponsor must conduct an evaluation of the UADE and must report the results of the evaluation to FDA, the IEC/IRB and participating Investigators within 10 working days after the Sponsor first receives notification of the effect.

##### **Non-Serious Adverse Events**

All non-serious adverse events, including non-serious adverse device effects, will be reported to the sponsor by the Investigator no later than 2 days from discovery.

#### **13.4.2. Reporting Adverse Events to the Responsible IEC/IRB and Health Authorities**

Adverse events that meet the IEC/IRB requirements for reporting must be reported within the IEC/IRB's written guidelines. Each clinical site will refer to and follow any guidelines set forth by their Approving IEC/IRB. Each clinical site will refer to and follow any guidelines set forth by their local governing Health Authorities.

The Sponsor will report applicable Adverse Events to the local health authorities according the written guidelines, including reporting timelines.

### 13.4.3. Event of Special Interest

None.

### 13.5. Reporting of Pregnancy

Subjects reporting pregnancy (by self-report) during the course of the study will be discontinued after the event is recorded as an Adverse Event. Once discontinued, pregnant participants and their fetuses will not be monitored for study related purposes. At the Investigator's discretion, the study participant may be followed by the Investigator through delivery. However, this data will not be collected as part of the clinical study database. Pregnant participants are not discontinued from contact lens or solution related studies for safety concerns, but due to general concerns relating to pregnancy and contact lens use. Specifically, pregnant women are discontinued due to fluctuations in refractive error and/or visual acuity that occur secondary to systemic hormonal changes, and not due to unforeseen health risks to the mother or fetus.

## 14. STATISTICAL METHODS

### 14.1. General Considerations

Statistical Analysis will be undertaken by the sponsor or under the authority of the sponsor. A general description of the statistical methods to be implemented in this clinical trial is outlined below.

All data summaries and statistical analyses will be performed using the SAS software Version 9.4 or higher (SAS Institute, Cary, NC). Throughout the analysis of data, the results for each subject/eye will be used when available for summarization and statistical analysis.

Summary tables (descriptive statistics and/or frequency tables) will be provided for all baseline variables, efficacy variables and safety variables as appropriate. Continuous variables will be summarized with descriptive statistics (n, mean, standard deviation [SD], median, minimum and maximum). Frequency count and percentage of subjects or eyes within each category will be provided for categorical data.

### 14.2. Sample Size Justification

The plan is to enroll 60 subjects with a target of 50 subjects to complete the study. This is a pilot study and the sample size was not based on any empirical power calculation. The power analysis for different scenarios of size effects ( $\Delta$ ) and inter-subject correlation ( $\rho$ ), assuming a common VAS comfort score variance of 25, are summarized below:

Table 4: Power Analysis for VAS comfort

$\Delta$	$\rho$	Power (%)
5	.30	21.6
	.50	28.4
	.80	59.2
10	.30	64.9
	.50	79.2
	.80	99.2

The power analysis was conducted the SAS procedure PROC POWER procedure for paired tests.

### 14.3. Analysis Populations

#### **Safety Population:**

All subjects who were administered any test article excluding subjects who drop out prior to administering any test article. At least one observation should be recorded.

#### **Per-Protocol Population:**

All subjects who have successfully completed all visits and did not substantially deviate from the protocol as determined by the trial cohort review committee prior to database hard lock (Per-Protocol Population). Justification of excluding subjects with protocol deviations in the per-protocol population set will be documented in a memo to file.

#### **Intent-to-Treat (ITT) Population:**

All randomized subjects regardless of actual treatment and subsequent withdrawal from study or deviation from protocol. At least one observation should be recorded.

### 14.4. Level of Statistical Significance

All planned analysis for this study will be conducted with an overall type I error rate of 5%.

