#### **Hypothesis Testing:**

The null and alternative hypotheses for superiority is as follows:  $H_0: \beta_3 \leq 0$ ,  $H_a: \beta_3 > 0$ . Superiority will be declared if the lower bound of the 2-sided 95% credible interval of the difference between Test and Control is greater than 0:  $P(\beta_3 > 0|y) \geq 0.95$ .

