#### **14.6. Secondary Analysis**

OSDI scores will be analyzed using the same model described in the primary analysis. The null and alternative hypotheses for superiority is as follows:  $H_0: \beta_3 \geq 0$ ,  $H_a: \beta_3 < 0$ . Superiority will be declared if the upper bound of the 2-sided 95% credible interval of the difference between Test and Control is less than 0:  $P(\beta_3 < 0|y) \geq 0.95$ .

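### Section 14.4 promises an overall 5% type I error, but the two ungated superiority claims (VAS, OSDI) keep it under only one of the two thresholds written in each success rule

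*Combined protocol and SAP*

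**What the plan says.** Section 14.4 sets one error rate for everything: "All planned analysis for this study will be conducted with an overall type I error rate of 5" percent. It does not say whether this is one- or two-sided, and it does not allocate it between endpoints.

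The Hypothesis Testing part of section 14.5 sets a one-directional null for VAS comfort. The claim is made if the "lower bound of the 2-sided 95% credible interval of the difference between Test and Control is greater than 0". After a colon, the same sentence adds the criterion "P(\beta_3 > 0|y) \geq 0.95".

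Section 14.6 applies the same model to OSDI with the direction reversed. The claim is made if the "upper bound of the 2-sided 95% credible interval of the difference between Test and Control is less than 0", and again a criterion follows: "P(\beta_3 < 0|y) \geq 0.95".

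Sections 2.2 and 2.3 label VAS primary and OSDI secondary and state a superiority hypothesis for each. Nothing in section 14 makes the OSDI claim depend on the VAS result. Section 2.3 also says that this is a pilot and that all its hypotheses are exploratory.

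**The concern.** An overall rate across all planned analyses reads as a rate for the set of claims, not for each claim. Two claims that can each be declared on their own add to the chance that at least one is false. Whether the total stays within 5% depends on the threshold per claim, and the plan writes two. A posterior probability between 0.95 and 0.975 would be a success under the formula and a failure under the interval.

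At stake is a declaration that Test is superior on VAS or OSDI, made more easily than section 14.4 says. Section 21 foresees use of the data in scientific materials, so such a claim could travel. There is also a practical gap. Section 14.7 starts the predictive-probability work when superiority is not concluded, without naming the endpoint, so it is unclear what happens if OSDI succeeds and VAS fails.

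**Working it through.** **Inputs.** Overall rate 5% (14.4). Two one-directional tests (14.5, 14.6). Thresholds 0.975 and 0.95 (same sections). Vague priors (14.5, The Model). No interim analysis (14.8), so no error is spent there. The correlation ρ between the two test statistics, taken in the direction that favours Test, is not in the documents and is varied as an assumption.

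**Step 1: thresholds as error rates.** With vague priors, a posterior probability is close to 1 minus a one-sided p-value.
- Posterior probability at least 0.95: a = 0.05 per test.
- Equal-tailed 2-sided 95% interval excluding 0: posterior probability above 0.975, so a = 0.025 per test. The plan does not say that the interval is equal-tailed; this is assumed.

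A rough simulation of the model (400 null trials, n = 50, SD 25, period correlation 0.5, no baseline term) gave per-test errors of 5.0% at 0.95 and about 3.3% at 0.975. The Monte Carlo standard error is about 1 point, so both results agree with 5% and 2.5%.

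**Step 2: two ungated tests, both nulls true.**
- Upper bound: a + a. This is 0.05 + 0.05 = 10% or 0.025 + 0.025 = 5.0%.
- Independent: 1 − (1 − a)². This is 1 − 0.95² = 9.75% or 1 − 0.975² = 4.94%.
- Correlated: 1 − Φ₂(c, c; ρ), where Φ₂ is the bivariate normal distribution function and c is the standard normal quantile at 1 − a.

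| Assumed ρ | Posterior ≥ 0.95 | 95% interval excludes 0 |
|---|---|---|
| 0 | 9.75% | 4.94% |
| 0.3 | 9.3% | 4.8% |
| 0.5 | 8.8% | 4.5% |
| 0.7 | 8.0% | 4.2% |
| 0.8 | 7.5% | 3.9% |
| 0.9 | 6.8% | 3.5% |

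Under the 0.95 rule the total comes down to 5% only at perfect correlation. If only one null is true, the chance of a false claim is that test's own rate, 5% or 2.5%.

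**Step 3: which threshold matches the plan's power figures?** Section 14.2 gives neither alpha nor sides for Table 4. Power was recomputed for a paired t test with n = 50, SD of the difference = 25 × √(2(1 − ρ)), where ρ is here Table 4's own correlation. (Section 14.2 says variance 25, but Table 4 reproduces only with SD 25, which is a separate matter.)
- Two-sided 0.05: 21.6, 28.4, 59.2, 64.9, 79.2, 99.2. All six cells of Table 4 match.
- One-sided 0.05: 32.1, 40.1, 71.2, 76.2, 87.4, 99.7. These do not reproduce the table.

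Table 4 therefore corresponds to the interval rule (0.025 in the direction of superiority), not to 0.95.

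**Step 4: effect of a fixed sequence.** Suppose OSDI can be declared only after VAS. If the VAS null is true, any false claim requires a false VAS claim first. If it is not true, only OSDI can be falsely claimed. In both cases the total is at most a: 5% at 0.95, or 2.5% at 0.975.

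**The case against.** The strongest reply is that the interval rule is the operative one. Section 14.5 says that inference rests on a posterior credible interval and that results are reported with 95% intervals, and Table 4 was computed at two-sided 0.05. On that reading two ungated tests cannot exceed 5.0% at any correlation, and section 14.4 is kept without a gate. This stands as an argument about likely intent. It does not remove the 0.95 criterion, which is written as the explicit formula in both sections and which an analyst could program as it is.

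Three stronger readings are tempting, and the documents do not support them.
- A reader might infer that the plan has an 8-10% error rate outright. That range needs the 0.95 rule and a correlation of about 0 to 0.7, and the documents do not give the correlation. Near-doubling of the 5% occurs only close to independence with both nulls true.
- A reader might infer that the interval rule also fails, because up to 4.94% is about twice the 2.5% of a single interval. The plan does not state 2.5% as its overall rate. Against the 5% that it does state, the interval rule complies.
- A reader might infer that confirmatory control is required here. Section 2.3 calls the hypotheses exploratory, and section 14.2 says that the sample size was not based on a power calculation. What remains is that the sponsor chose to promise an overall rate and to declare superiority, so the two should agree.

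**Conclusion.** The point holds conditionally. The success rule in sections 14.5 and 14.6 contradicts itself, and the 5% in section 14.4 is true under only one of its two halves. Under the 0.95 criterion the chance of at least one false superiority claim is about 7-10% for assumed correlations from 0.9 down to 0; under the interval criterion it is at most 5.0%. These figures assume that both nulls are true, that vague-prior posterior probabilities behave like one-sided p-values, and that the interval is equal-tailed. Severity is low in a pilot with exploratory hypotheses.

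**What to change.** 1. In sections 14.5 and 14.6 keep one threshold. The consistent choice is to replace 0.95 with 0.975 in both formulas, which matches the 95% interval and Table 4.
2. Add to section 14.6: *OSDI superiority will be declared only if VAS superiority has been declared; otherwise OSDI will be reported with its 95% credible interval and no superiority claim.* This follows the existing primary and secondary order. With 0.975 the gate is not needed to keep the total within 5%; if 0.95 is kept, it is essential.
3. In section 14.4 state whether the 5% covers the pair of claims and whether it is one- or two-sided.

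The cost is a few words and one added sentence, with no change to data collection. The downside is that OSDI superiority cannot be claimed if VAS fails. The 0.975 threshold has less power than 0.95 (for a difference of 10 and Table 4 correlation 0.5, 79.2% against 87.4%), but 79.2% is the figure that Table 4 already gives, so nothing is lost against the stated power.
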